2.2.3.1 Aveir LP

Intended Use: The Aveir™ LP (model LSP201A - right atrial and LSP202V - right ventricular) is designed to provide bradycardia pacing as a pulse generator with built-in battery and electrodes for implantation in the right ventricle and/or right atrium. The LP is intended to provide sensing of cardiac signals and delivery of cardiac pacing therapy within the implanted chamber for the target treatment group. The LP is also intended to operate optionally with another co-implanted LP to provide dual-chamber pacing therapy.

As a leadless device, the Aveir LP does not need a connector, pacing lead, or pulse generator pocket. The LP is delivered to the target heart chamber percutaneously via the femoral vein through an Aveir Introducer and Aveir Delivery Catheter. The proximal end of the LP has a feature for docking to delivery and retrieval catheters, providing for repositioning and retrieval capability. A distal non-retractable, helix affixes the LP to the endocardium of the target heart chamber. Three additional features on the outside of the LP nosecone are designed to provide secondary fixation securement.

Sensing and pacing occur between a distal electrode near the fixation helix and the external can of the LP. The tip electrode includes a single dose of dexamethasone sodium phosphate (DSP), intended to reduce inflammation. The distal tip electrode is a titanium-nitride coated platinum-iridium disc located at the center of the fixation helix. The ring electrode is the uncoated proximal part of the titanium pacemaker case.

The LP senses local blood pool temperature to provide rate modulated pacing with changes in metabolic demand.

Communication Between Co-Implanted Leadless Pacemakers

To allow dual-chamber synchronous sensing and pacing to occur, each LP communicates bidirectionally with the programmer system and also beat-to-beat with a paired, co-implanted LP. Through i2i™ (implant-to-implant) communication via two electrodes on each LP, electrical signals are output with data encoded in a series of short pulses delivered concurrently with each local paced or sensed event.

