Generally, in a dual-chamber operating mode, the RV-implanted LP manages overall pacing and timing functions, while the pacing and timing functions of the RA-implanted LP are managed indirectly by the RV-implanted LP. The RV-implanted LP's activity sensor determines the target sensor-indicated rate to be used by both LPs and the rate is set (or updated) through i2i communication.

In the event of a sustained disruption in communication between the co-implanted LPs, the system will automatically revert to ventricular-only pacing mode until communication is restored.

Communication Between Leadless Pacemaker and Programmer

Clinical Investigation Plan for Europe

Each LP communicates bi-directionally with the external Aveir Link Module in conjunction with a Merlin Patient Care System (PCS) Model 3650 programmer to interrogate and program the LP and to monitor electrocardiogram (ECG) waveforms for observing LP function.

The Link Module provides an interface between the Merlin Programmer and standard ECG electrodes placed on the subject's torso, for two-way communication with the implanted LP(s) and acquisition of the surface ECG. The Programmer transmits signals to an implanted LP via conducted communication with sub-threshold electrical pulses applied via skin electrodes.

Consequently, the LP transmits signals using circuits and electrodes already provided for pacing, with data encoded in pulses delivered during the heart's refractory period. This conducted communication allows data to be communicated between the LP and surface electrodes at a low current that does not affect pacing or sensing functions. The LP also has a commanded electrogram (EGM) for current of injury assessment. An EGM shows the heart's electrical activity as sensed by the pacing system. The current of injury is a measure intended to assess implant integrity during the implant procedure, like conventional transvenous leads.

Each Aveir LP is supplied contained inside a Loading Tool to hold the LP until the implantation procedure. The Loading Tool with the LP facilitates connection of the LP to the Delivery Catheter. The Loading Tool does not have direct patient contact. Figure 1 and Table 2 below show the Loading Tool and features of both Aveir LPs.

[figure not shown]
Clinical Investigation Plan for Europe

Figure 1 - Loading Tool and LPs

LP packaged in Loading Tool

Aveir LP (Right Atrial)

Aveir LP (Right Ventricular)

[figure not shown]

Table 2 – LP Features

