6.6.2.1 AV Synchrony Assessment – In-Clinic

Subject Population

All *de novo* subjects who can be programmed to a dual chamber pacing mode will be administered the in-clinic AV Synchrony Assessment.

Setup

³ Administration of the CAEP protocol can be done any time between the 3- month and 6-month follow-up visit until 30 subjects contribute to the analysis

⁴ Holter data collection can be done any time between the 3- month and 6-month follow-up visit.

Clinical Investigation Plan for Europe

After the 3-month LP Assessment and Programming is performed and device session printouts obtained, the site will clear the device diagnostics prior to starting the in-clinic AV Synchrony Assessment.

A Holter monitor will be setup and worn by the subject according to the instructions provided by the Sponsor and/or Core Lab. The setup may include adjusting the clock times on the Holter Monitor or Merlin Programmer so that the beginning and end of each position/activity can be identified on both devices.

The subject will also be connected to the Merlin Programmer at certain periods during the assessment. The investigator may also need to reprogram the base rate to improve the likelihood of atrial pacing for select patients. LP interrogation and Holter recording should not take place simultaneously to minimize device artifacts or noise on the Holter.

The site will be trained to properly set up the Holter and Merlin Programmer for the in-clinic AV Synchrony Assessment through separate instructional materials.

AV Synchrony Assessment For Primary Effectiveness Endpoint #2:

While wearing the Holter monitor, the subject should remain in a seated position at rest for 5 minutes while the Holter will record the subject's cardiac rhythm. The site will record the Holter start and stop recording times on the AV Synchrony Assessment CRF and then interrogate the LP. At the end of the assessment period, the site will obtain a device session printout. The site will be trained to administer the in-clinic AV Synchrony Assessment and send the Holter data to the Core Lab for AV Synchrony analysis.

The Sponsor will evaluate the data from this assessment for the primary effectiveness endpoint #2.

Additional AV Synchrony Assessment in Various Positions/Activity Levels:

While wearing the Holter monitor, the subject's cardiac rhythm will be recorded while the subject assumes the following positions and activity levels in the following order for 2 minutes each:

- Supine
- Left Lateral

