associated with each pacing stimulus. The pacing stimulus may stimulate the diaphragm either directly or indirectly via the phrenic nerve.

Dislodgement: The LP separates from the endocardium after the implant procedure has been completed.

Elevated Pacing Thresholds (RV): Pacing thresholds > 2.5 V at 0.4 ms at implant. Following lead maturation at 6-8 weeks, an increase in pacing thresholds of 1.2 V at 0.4 ms or greater between visits. This definition is intended to serve as a guideline and it is understood that individual subjects may have unique situations.

Elevated Pacing Thresholds (RA): Atrial pacing thresholds > 4.0 V at 0.4ms on or after the pre-discharge assessment, or if there is an increase in atrial pacing thresholds of 1.2V at 0.4 ms or greater between visits. This definition is intended to serve as a guideline and it is understood that individual subjects may have unique situations.

Established i2i Communication: A situation at the end of an implant procedure where non-zero i2i throughput in either LP transmission direction (i.e. A2V or V2A) has been demonstrated. If any of the following situations occur, i2i communication will NOT be considered established:

- a) Implanter decides to retrieve 1 or 2 LPs and not replace them exclusively due to unacceptable i2i communication; OR
- b) Implanter deliberately programs the LPs to a non-dual chamber pacing mode due to unacceptable i2i communication; OR
- c) There is zero i2i throughput in both LP transmission directions (i.e. atrial LP to ventricular LP AND ventricular LP to atrial LP)

Intermittent or loss of i2i communication: When the subject either (a) has their Aveir DR system programmed to a non-dual chamber pacing mode at the end of any pre-discharge or follow-up visit solely due to unsatisfactory i2i communication even in the absence of untoward clinical signs, or (b) undergoes a system revision intervention due to unsatisfactory i2i communication.

Implant procedure duration: Defined as the time from delivery catheter and LP insertion to removal.

Implant success rate: Defined as the number of *de novo* subjects leaving the implant procedure with both implanted and functioning LP devices, divided by the number of subjects in whom implantation is attempted.

Inadequate Fixation: When an LP separates from the endocardium after being released from the Delivery Catheter during the implant procedure.

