2.3.3 Primary Effectiveness Endpoint #2 Analysis

The primary effectiveness endpoint #2 evaluates the 3-month AV synchrony success rate ($Rate_{AV}$) at rest while sitting using a Holter monitor in-clinic.

AV synchrony success is defined as subjects with a paced or sensed ventricular beat within 300 ms following a paced or sensed atrial beat for at least 70% of evaluable cardiac cycles.

The primary effectiveness endpoint #2 hypothesis is:

$$H_0: Rate_{AV} \leq 83\% \quad \text{vs.} \quad H_1: Rate_{AV} > 83\%$$

where 83% is the performance goal. The $Rate_{AV}$ is the proportion of subjects who met success criteria in the primary effectiveness endpoint #2.

The $Rate_{AV}$ will be estimated as a binomial proportion and the 97.5% LCB of the $Rate_{AV}$ will be calculated using the normal approximation. The null hypothesis is rejected at the 2.5% significance level if the LCB exceeds the PG of 83%. The p-value for the one-sided Z-test will be calculated and compared to the 2.5% significance level.

The primary analysis for the primary effectiveness endpoint #2 will be based on subjects in the full analysis population. Subjects with unsuccessful implant solely due to a failure to establish i2i communication at end of implant procedure will be included and imputed as failures. Subjects with unsuccessful implants due to reasons other than AV synchrony (e.g., cardiac anatomy) will be excluded from this analysis.

Statistical Analysis Plan

Additionally, among the implanted population only the AV synchrony data available for evaluation will be used.

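### A subject taken out of dual-chamber mode for i2i reasons between implant and month 3 is missing, not a failure, in primary effectiveness endpoint #2; the one-direction definition of established i2i widens this gap

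*Protocol*

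**What the plan says.** **Implant-day label.** Under CIP Appendix II, i2i is established at the end of the procedure when "non-zero i2i throughput in either LP transmission direction (i.e. A2V or V2A) has been demonstrated". No minimum level is set. Three situations count as not established. Item (a) concerns retrieval: "Implanter decides to retrieve 1 or 2 LPs and not replace them exclusively due to unacceptable i2i communication". Item (b) concerns the mode chosen in the lab: "Implanter deliberately programs the LPs to a non-dual chamber pacing mode due to unacceptable i2i communication". Item (c) is the only one that rests on a throughput reading: "There is zero i2i throughput in both LP transmission directions". A successful implant needs two functioning leadless pacemakers (LPs) and established i2i.

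**Later loss.** Appendix II separately defines intermittent or lost i2i. It covers a subject left in a non-dual mode at a pre-discharge or follow-up visit solely because of the link, and a subject revised because of it.

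**Device description (CIP 2.2.3.1).** "each LP communicates bidirectionally with the programmer system and also beat-to-beat with a paired, co-implanted LP". In dual-chamber operation, "the pacing and timing functions of the RA-implanted LP are managed indirectly by the RV-implanted LP".

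**Endpoint #2 failures.** CIP 8.2.3 has two limbs: not meeting the AV synchrony criterion at 3 months, or an unsuccessful implant caused only by failure to establish i2i. SAP 2.3.3 restates the second limb: those whose procedure did not succeed "solely due to a failure to establish i2i communication at end of implant procedure will be included and imputed as failures". Among implanted subjects it otherwise uses only the synchrony data that are available. SAP 2.8 adds a tipping-point sensitivity analysis for missing results.

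**Who is tested.** CIP 6.6.2 limits the in-clinic assessment to *de novo* subjects who are programmed in a dual-chamber mode. CIP 6.6.2.1 words it differently, for the whole *de novo* group: "subjects who can be programmed to a dual chamber pacing mode will be administered the in-clinic AV Synchrony Assessment".

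**The concern.** Endpoint #2 asks whether the paired system keeps AV synchrony. A system that cannot hold the link well enough to stay in dual-chamber mode has failed at that task, and the plan accepts this when the failure is recognised during the implant procedure. It does not carry the same logic forward to month 3.

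Two features combine. The one-direction rule lets a system with a partial link leave the lab as a successful implant. The testing and available-data rules then let that subject, or one whose link was sound at implant and failed later, disappear from numerator and denominator if dual mode is abandoned before the assessment. Missingness is then caused by the failure being measured, so the bias favours the device. At stake is a primary endpoint judged against a fixed goal of 83% in a single-arm trial, where no control arm would lose subjects in the same way.

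**Working it through.** **1. Following one subject through the rules.** Take a subject with two LPs and a poor link.

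| When i2i leads to loss of dual mode | Implant-day label | Month-3 test | Primary analysis |
|---|---|---|---|
| In the implant lab | Not established, item (a) or (b) | Does not matter | Failure (imputed) |
| Pre-discharge (CIP 6.5.2: at most 2 days after implant) or any later visit before month 3 | Established if throughput was non-zero in one direction | Not under 6.6.2; under 6.6.2.1 only if dual mode can be programmed | Not counted if untested |
| Never; still in dual mode at month 3 | Established | Yes | Holter result decides |

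The first two rows can describe the same device behaviour a day or two apart. The second row meets Appendix II's own definition of intermittent or lost i2i, but neither CIP 8.2.3 nor SAP 2.3.3 uses that definition.

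**2. The pass mark.** Inputs: 267 evaluable subjects (CIP 8.3, SAP 2.4), goal 83%, one-sided 2.5%, normal-approximation lower bound (SAP 2.3.3). The assumed success rate and the power are blacked out, so 267 cannot be reproduced. It equals 300 × 0.89, that is 11% attrition, but this is inferred.

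LCB = p − 1.96 × √(p(1 − p)/n)

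- 232/267: p = 86.89%, SE = 2.065 points, LCB = 82.84%, fail
- 233/267: p = 87.27%, SE = 2.040 points, LCB = 83.27%, pass

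The pass mark is 233.

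**3. Counting the omitted subjects as failures.** They add to the denominator only.

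- One subject: 233/268 = 86.94%, SE = 2.058 points, LCB = 82.91%, fail
- Three subjects: 233/270 = 86.30%, SE = 2.093 points, LCB = 82.19%, fail

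If the Z-test uses the variance under the null, the pass mark is 234: z = (234/267 − 0.83)/√(0.83 × 0.17/267) = 2.02. One added failure gives z = (234/268 − 0.83)/√(0.83 × 0.17/268) = 1.88, below 1.96. The conclusion is the same.

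**4. Away from the pass mark.** Let k be the number of omitted subjects, with 267 others tested. Both k and the true rate in the others are assumptions. Power is the exact binomial probability of reaching the required number among the 267.

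| k counted as failures | Needed | Share of the other 267 | Power at 90% | Power at 92% |
|---|---|---|---|---|
| 0 | 233/267 | 87.3% | 94.0% | 99.7% |
| 3 | 235/270 | 88.0% | 88.0% | 99.1% |
| 5 | 237/272 | 88.8% | 78.4% | 97.6% |
| 10 | 241/277 | 90.3% | 49.5% | 87.5% |

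Under the present rule, all k subjects drop out and the first row applies whatever k is.

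**The case against.** A reader might infer that a one-way system escapes the endpoint's failure rule altogether. The documents do not support that. It avoids only the implant-day limb; if it is still in dual mode at month 3 it is tested and fails if it does not meet the criterion, and the definition then makes no difference. Items (a) and (b) also already catch i2i-driven retrieval without replacement or non-dual programming at implant, whatever the throughput.

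A reader might also infer that the either-direction wording contradicts the device description. CIP 2.2.3.1 points that way, since the ventricular LP manages atrial timing through i2i, but it does not say how the system performs with traffic in one direction. In that section, two-way communication is stated explicitly for the programmer link. It also foresees communication being disrupted and restored, so zero throughput in one direction at the end of implant need not be permanent.

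The arithmetic is driven by the available-data rule more than by the word *either*: a system with a two-way link at implant that loses it later drops out in the same way. The 233/268 example also starts exactly on the pass mark, where any single failure changes the result. Both points stand, which is why changing that one word would not be enough.

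It could be argued that an untested subject has not met the month-3 criterion and so already fails under CIP 8.2.3. SAP 2.3.3 and 2.8 read otherwise: such a subject is missing and is examined by tipping point. That sensitivity analysis is a real safeguard, but it does not change the primary result and does not separate link failures from missed visits.

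Finally, the implant-day imputation can override a genuine month-3 success, and a reader might call that an error. Because sensed beats count, a subject with intact conduction can pass the Holter without a working link, so the imputation is a defensible conservative rule.

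**Conclusion.** The point holds in a limited form. Subjects with an absent, one-way or lost link who leave dual-chamber mode for i2i reasons after the procedure and before month 3 have no failure classification in the primary analysis of endpoint #2. If untested they are missing, and the error favours the device.

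The size is conditional. The documents do not give the number of such subjects. At the pass mark one is enough to reverse the conclusion. With an assumed true rate of 90% in the others, counting 3 as failures lowers power from 94.0% to 88.0%, and counting 5 lowers it to 78.4%. At 92% the changes are small: 99.7% to 99.1% and 97.6%. If there are no such subjects, or all are tested, there is no effect.

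This rests on the readable text of CIP 8.2.3, SAP 2.3.3 and SAP 2.8. Blacked-out parts, including the assumed rate and power, are not treated as missing. The change should be made before the endpoint is analysed, because it affects a primary endpoint and costs little.

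**What to change.** 1. In CIP 8.2.3 and SAP 2.3.3, count as a failure any subject without a valid month-3 Holter result who either (i) had zero i2i throughput in either direction at the end of the implant procedure, or (ii) met the existing Appendix II definition of intermittent or lost i2i before the month-3 assessment.
2. Keep the present implant-day imputation in the primary analysis. Report, as a sensitivity analysis, the result when a valid month-3 Holter overrides it.
3. Reconcile the either-direction wording in Appendix II with the device description in CIP 2.2.3.1.
4. Reconcile CIP 6.6.2 (programmed in dual mode) with CIP 6.6.2.1 (can be programmed to it), so that the population to be tested is stated once.

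Cost: wording only. Throughput for both LPs is already recorded at implant and follow-up (CIP 6.2.5). The reported success rate may be slightly lower, and item (i) will also count a one-way subject whose month-3 result is missing for an unrelated reason. The change concerns endpoint classification only; it does not touch device programming or patient management.

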Sponsor understands that the following items meet the definition of serious adverse event if they require hospitalization or prolong hospitalization, even though an invasive approach may not be necessary to resolve: AV fistula, pseudoaneurysm, blood transfusions, tricuspid valve damage, pericardial effusion, pulmonary embolus, device dislodgement, right ventricular or right atrial perforation, thrombus formation on the device, ventricular arrhythmias even if not associated with an invasive strategy to remedy.

Non-invasive means such as device re-programming do not meet the criteria for medical or surgical intervention.

Successful Implant: A subject who leaves an attempted *de novo* implant procedure with functioning atrial and ventricular LPs implanted, including established i2i communication

Clinical Investigation Plan for Europe

Successful Upgrade: A subject with a pre-existing Aveir ventricular LP who was successfully implanted with an Aveir atrial LP, and the Aveir VR LP can be programmed to a dual-chamber mode

Time to discharge: Defined as the time from introducer sheath removal to discharge.

Unanticipated (serious) adverse device effect (UADE/USADE): Any serious adverse effect on health or safety or any life-threatening problem or death caused by, or associated with, a device, if that effect, problem, or death was not previously identified in nature, severity, or degree of incidence in the investigational plan or application (including a supplementary plan or application), or any other unanticipated serious problem associated with a device that relates to the rights, safety, or welfare of subjects. [21 CFR 812.3(s)]

Unavoidable adverse event: An unavoidable AE is defined as an adverse event related to the implant procedure that is expected to occur for a projected duration in all subjects.

Undersensing: The failure of the pulse generator to sense R-waves, causing delivery of inappropriately timed, asynchronous or competitive output pulses. Undersensing can sometimes be corrected by programming the device to a more sensitive setting, i.e., decreasing the millivolt value.

Unsuccessful Implant: A subject who leaves an attempted *de novo* implant procedure without a functioning atrial or ventricular LP implanted, or where i2i communication was not established.

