3.5 Additional Data

The following additional data will be recorded and reported descriptively:

- Comparisons of demographics between the study population to the existing dual-chamber pacemaker population by region
- All adverse events, and whether or not each is device-related or procedure-related
- Implant success rate and reasons for unsuccessful implant

Statistical Analysis Plan

- Device handling characteristics at implant
- Number of device repositioning at time of implantation
- Implant duration, fluoroscopy duration, and time from implant to hospital discharge
- Pre-procedure (i.e. MRI, CT, X-ray) and procedural imaging (i.e. ICE) measures to evaluate the right atrium and/or the atrial LP based on any imaging data provided to the Sponsor
- Final location of LP placement
- Demographics: gender, age, ethnicity, race, indication for pacemaker implant
- Medical history
- Use of beta blocker, ACE, ARB, anti-coagulation, anti-arrhythmic, and anti-platelet medications
- Remaining device longevity at the six-month visit, as displayed by the programmer based on delivered therapy, programmed settings, percent pacing, and measured pacing impedance.
- Average base rate, impedance, pulse amplitude, pulse duration and percentage pacing will also be reported for all visits
- Hospitalizations
- Mortality
- Upgradeability of the Aveir ventricular LP (VR) into the Aveir DR LP system summarized by:
 - Success rate of VR to DR upgrades and reasons for unsuccessful upgrades.
 - Summary of adverse events related to upgrades
 - Summary of device measurements for subjects with an upgrade
- AV synchrony (at various positions and activity levels)
- EQ-5D Health-Related Quality of Life Analysis

3.6 24-Hour Holter Monitor Data Analysis

All capable *de novo* subjects will be asked to wear a 24-hour Holter monitor and complete a symptom diary, until 50 subjects provide data contributing to the analysis. The test may be performed any time after the beginning of the 3-month visit window. The preferred window to perform the 24-hour Holter test is between the 3-month and 6-month visit. These data will be examined for appropriate sensing, pacing, AV Synchrony during the activities of daily living for each subject. In addition, these data will be evaluated for any correlation between any subject symptoms with losses of AV synchrony, if present.

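### The descriptive implant success rate leaves out established i2i communication, which the plan's own definition of a successful implant requires

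*Protocol*

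**What the plan says.** Four places bear on this.

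- **Rate.** Protocol Appendix II restricts the numerator of the implant success rate to de novo patients and words the rate this way: "subjects leaving the implant procedure with both implanted and functioning LP devices, divided by the number of subjects in whom implantation is attempted".
- **Successful Implant.** The same appendix requires the subject to leave the procedure with "functioning atrial and ventricular LPs implanted, including established i2i communication".
- **Unsuccessful Implant.** This is a subject who leaves "without a functioning atrial or ventricular LP implanted, or where i2i communication was not established".
- **Reporting.** SAP 3.5 lists "Implant success rate and reasons for unsuccessful implant" as a single item of additional data, and Protocol 4.3 has the same item. The readable SAP text gives no definition of the rate of its own.

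Appendix II also says when i2i counts as not established. There are three routes: (a) "Implanter decides to retrieve 1 or 2 LPs and not replace them exclusively due to unacceptable i2i communication"; (b) "Implanter deliberately programs the LPs to a non-dual chamber pacing mode due to unacceptable i2i communication"; (c) "There is zero i2i throughput in both LP transmission directions".

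Protocol 8.2.3 and SAP 2.3.3 treat a subject whose implant is unsuccessful solely because i2i was not established as a failure of primary effectiveness endpoint #2. Protocol 4.3 says that the additional data are summarised descriptively, without hypothesis tests.

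**The concern.** Two rules in one appendix classify the same subject differently, and both feed one line of the report. A reader who sees a success rate beside a list of reasons for unsuccessful implant will expect the listed subjects to be those missing from the numerator. With the definitions as they stand, i2i failure can appear as a reason for a subject who has also been counted as a success.

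The omitted condition matters for this device. Protocol 2.2.3.1 describes i2i as what allows the two LPs to sense and pace synchronously, and says that a sustained loss of communication puts the system into ventricular-only pacing. A rate that ignores i2i measures whether two devices were placed and work in their own chambers. It does not measure whether the subject left with a working dual-chamber system.

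**Working it through.** The documents state no implant success figure, expected value or power for this rate, so there is no plan figure to reproduce. The check compares the definitions and then sizes the gap.

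**Step 1. Classify each kind of subject under both rules.**

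| Status at the end of a de novo implant procedure | In the rate's numerator? | Appendix II class |
|---|---|---|
| Two functioning LPs, i2i established | Yes | Successful |
| Two functioning LPs kept, non-dual-chamber mode because of i2i (route b) | Yes | Unsuccessful |
| Two functioning LPs kept, zero throughput both ways (route c) | Yes | Unsuccessful |
| One or both LPs retrieved and not replaced because of i2i (route a) | No | Unsuccessful |
| An LP absent or not functioning for another reason | No | Unsuccessful |

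The rules disagree only in rows two and three. Protocol 6.2.4 allows for such cases: when both LPs are in place, dual-chamber pairing has to be attempted, and discharge in a dual-chamber mode depends on its being verified.

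**Step 2. Compare with the parallel definition for upgrades.** In Appendix II, both Successful Upgrade and the upgrade success rate require that the system can be programmed to a dual-chamber mode. The subject-level definition and the rate agree there. Only the de novo rate has lost the condition.

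**Step 3. Size the gap.** Let N be the number of attempted de novo implants, S the number with two functioning LPs, and k the number of those S without established i2i.

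- Rate as defined: S/N
- Share meeting Successful Implant: (S − k)/N
- Difference: k/N

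Take N = 300, the planned number of de novo subjects for the primary endpoints (Protocol 5.6), on the assumption that all have an attempted implant. S = 294 and all values of k are also assumptions.

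| k (assumed) | Rate as defined | Share meeting Successful Implant | Gap (points) |
|---|---|---|---|
| 0 | 294/300 = 98.0% | 294/300 = 98.0% | 0 |
| 3 | 98.0% | 291/300 = 97.0% | 1.0 |
| 6 | 98.0% | 288/300 = 96.0% | 2.0 |
| 9 | 98.0% | 285/300 = 95.0% | 3.0 |

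The gap does not depend on S. If the up to 200 further de novo subjects in Protocol 5.6 were included, N could reach 300 + 200 = 500, and k = 3 would give 3/500 = 0.6 points.

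**Step 4. Check the reconciliation.** The rate implies N − S unsuccessful implants, here 300 − 294 = 6. A listing that follows the Unsuccessful Implant definition holds N − S + k. With k = 3 that is 9 subjects against an implied 6.

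**The case against.** The strongest textual defence is that functioning already covers i2i. Successful Implant can be read that way, since it introduces i2i with the word including, and the documents never define functioning. But Unsuccessful Implant joins the i2i condition to the functioning-LP condition with or, as a separate route to failure. That would be redundant if functioning already included i2i. The defence is weak.

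Other objections stand and limit the point.

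- **No mismatch is certain.** It needs at least one subject by route (b) or (c). Route (a) subjects fail under both rules.
- **The final table cannot be seen.** The SAP refers to table mockups, and its section 7.0 is redacted. The output may already separate i2i.
- **The rate carries no inferential weight.** It is descriptive, and no imputation rule uses it.

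A reader might infer that this rate is the only place where implant failures show. The documents do not support that. The reasons for unsuccessful implant are reported, complications that prevent implantation count in the primary safety endpoint (Protocol 4.1.1), and Unsuccessful Implant is a listed reason for discontinuation (Protocol 5.5), with early-termination reasons summarised under SAP 3.3. Subjects who fail solely through i2i are not dropped from primary effectiveness endpoint #2 either. They are counted as failures there.

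A reader might also take the denominator literally, because it does not repeat de novo, and count attempted upgrades in it. With all 50 upgrade subjects included, the assumed 294 would give 294/(300 + 50) = 84.0%, which lowers the rate. That reading is strained: Appendix II gives upgrades a separate rate with its own denominator. The missing words need only a clarification.

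**Conclusion.** The inconsistency is real but minor. As written, the implant success rate counts as successes any de novo subjects who keep two functioning LPs without established i2i, although the plan's own definitions make them Unsuccessful Implants. The rate then exceeds the share meeting Successful Implant by k/N: 1.0 point for an assumed 3 of 300, and nothing if k = 0. The documents offer no basis for predicting k, so the size is illustrative.

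The conclusion rests on reading functioning as not including i2i, which the wording of Unsuccessful Implant supports. It does not extend to the confirmatory results. The rule for primary effectiveness endpoint #2 uses the unsuccessful-implant wording and already counts these subjects as failures. No hypothesis test, performance goal or sample size changes.

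**What to change.** In Protocol Appendix II, define the implant success rate as the number of de novo subjects meeting Successful Implant, including established i2i, divided by the number of de novo subjects with an attempted implant. Carry that definition into SAP 3.5. Stating de novo in the denominator also settles the wording there.

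Report the proportion leaving with two functioning LPs regardless of i2i as a separate, labelled line. The difference between the two lines is then k/N, and the listed reasons for unsuccessful implant reconcile with the success rate.

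The cost is one definition and one table row. No new data are needed, because i2i throughput is already recorded at implant (Protocol 6.2.5) and the reasons for an unsuccessful implant go on the Implant Form. The downside for the sponsor is a reported rate that may be slightly lower.
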